
Alcohol Administration. Alcohol administration procedures are consistent with those used by Drs. [name] and [name] in their previous work, as well as NIAAA guidelines for the safe and ethical administration of alcohol in experimental settings (Brown et al., 2014). Participants will complete two laboratory sessions in which they will be administered one of two beverages: placebo (0.00 g/dL target BrAC) or active alcohol (0.08 g/dL target BrAC). Session order will be counterbalanced across participants. For laboratory sessions in which a participant will be given the active dose, the quantity of medical grade alcohol (100% or 95% ethanol) needed to achieve 0.08 g/dL will be calculated using a modification of the Widmark formula. The medical (United States Pharmacopeia) grade ethanol used in this study will be obtained from standard laboratory supply providers (e.g., Fisher Scientific). The Widmark formula

utilizes age and weight measures for men and height and weight measures for women (Watson, et al., 1981; Widmark, 1932). Only research assistants over the age of 21 will be involved in drink mixing/administration procedures, and all research assistants will be trained by the PI in drink mixing/administration procedures. In order to maintain the study's double blind, a researcher not involved in QST will be responsible for calculating alcohol doses and mixing drinks, and the dose calculation and mixing procedure confirmed by a second research assistant. Alcohol will be mixed with ice-cold sugar-free lemon-lime soda in a 1:3 ratio and split into two servings ([name], et al., 2014; Gilbertson, et al., 2009; Harrison et al., 2007). Placebo beverages will consist of only vehicle. Participants will consume both servings within 5 minutes, and both active and placebo drinks will be misted with alcohol to enhance placebo effectiveness. A small amount of alcohol will be placed on the rim of the glass and the surface of the drink in order to further mask the study condition. Participants will rinse their mouths thoroughly with water once their beverage has been consumed. To avoid influencing participants' expectations regarding alcohol analgesia, no suggestion regarding the potential pain-relieving effects of alcohol will be provided before or after beverage administration.

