fMRI Heat Pain Protocol. Three task-based fMRI runs will be conducted subsequent to resting-state scanning using a noxious thermal stimulation protocol. This protocol has been previously used in an NIH-funded study in which [name] is a co-investigator (R01AT006334). For this task, a long MR-compatible thermal probe attached to a Medoc Q-Sense fMRI compatible thermal stimulator will be used to deliver noxious thermal stimuli. Blocks of thermal stimuli will be delivered to the glabrous skin of the foot at the individually calibrated temperature determined during the screening visit. Following each thermal stimulation block, participants will rate levels of pain intensity and perceived relief from alcohol. Each block will be preceded and/or followed by a 30-second rest blocks. An electronic VAS will be presented following each thermal stimulation block for the purposes of rating pain intensity (anchored from "No pain at all" to "Most intense pain imaginable"). After each run, participants will rate their perceived degree of relief from pain as a result of consuming their beverage using an electronic

VAS anchored from “No relief at all” to “Most profound relief imaginable”. Runs will last for approximately 6 minutes, and will take place consecutively.

Power Analysis. Power analysis and recruitment goals are based on results of our pilot study (see attached grant document for a detailed description of results). Power analyses were performed assuming two-tailed hypothesis tests. Effect sizes are reported as Cohen’s d, r, or f^2 (Cohen, 1988).

Our pilot data suggested statistically large increases in pain threshold temperature ($d = 1.16$) associated with BrACs $\sim .052$ g/dL. Effects on pain tolerance temperature and intensity ratings were smaller ($d = .28$); however, our targeted sample of 110 completers will provide $\sim 80\%$ power these effects, and $> 99\%$ power to detect effects of alcohol on pain threshold.

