FH of alcoholism was associated with greater expectancy of pain relief from alcohol intake in our pilot work ($d = 1.12$), as well as lower ratings of pain relief ($d = .54$). Effects of sex on these measures were large ($d > .88$). Sex also appeared to be a potent moderator of alcohol analgesia ($d > .90$), with women showing stronger analgesic effects. Our sample will provide $> 80\%$ power to detect these effects. FH was associated with smaller effects on alcohol-related reductions in pain intensity ($d = .42$), as well as pain threshold and tolerance ($d < .26$), resulting in $\sim 54\%$ power to detect interactive effects of FH and dose on these measures.

Across participants, preliminary data suggested small-to-moderate correlations between expectancy of pain relief from alcohol, ratings of pain relief, and typical daily drinking and reductions in pain sensitivity ($.26 < r < .44$). We anticipate $\sim 80\text{-}99\%$ power to detect these effects. However, our data also suggested that sex and FH may moderate these relationships. The interaction of sex and expectancy of pain relief strongly predicted increases in pain threshold and tolerance associated with alcohol intake ($f^2 > 1.11$). A similar effect was detected for the interaction of FH and expectancy of pain relief ($f^2 > .81$). A weaker interaction of FH and ratings of relief on QST measures was also detected ($f^2 > .37$). Likewise, interactions of sex with typical daily drinking and ratings of relief showed some relation to QST changes ($f^2 < .21$). We anticipate $> 94\%$ power to detect each of these interactions. There was little evidence of Sex or FH interactions with typical drinking on alcohol analgesia ($f^2 < .04$). Effect sizes of FH X Sex X expectancy/relief/typical drinking interactions could not be assessed given our limited sample; however, we anticipate sensitivity to detect an interactive $f^2 > .14$ with 80% power given our recruitment target.

Data Analysis Strategy. Data will be analyzed using SPSS 24 (IBM Corp., Armonk, NY).

Aim 1. Test competing hypotheses regarding the effects of family history of alcoholism on alcohol analgesia. To assess hypotheses related to Aim 1, FH status will be included as an independent variable in repeated measures general linear models analyses (rmGLM; SPSS GLM procedure; repeated: dose), with pain threshold/tolerance and intensity ratings, associated relief ratings, expectancy of pain

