relief from alcohol, and SEAS measures (i.e., HIGH+, HIGH-, LOW+, and LOW-; Morean et al., 2013, 2015) as dependent variables. Demographic, personality/affective (i.e., BDI/STAI/IRQ/NEO-derived neuroticism), and biomedical (i.e., menstrual phase for female participants, sleep quality) variables will be included as covariates should any be found to correlate significantly with magnitude of alcohol analgesia or relief ratings. A main effect of FH status such that FH+ individuals have greater magnitude of alcohol analgesia (i.e., greater increases in pain threshold/tolerance and decreases in pain intensity ratings), more positive/fewer negative subjective alcohol effects, and stronger expectancy of pain relief from alcohol consumption will be interpreted as evidence in support of H1 and H3. Lower ratings of alcohol-related relief from pain in FH+ individuals will provide support for H2.

To determine the independent contributions of expectancies and typical drinking behavior to alcohol analgesia, these measures will be included as independent variables in separate multiple regression analyses including interaction vectors with sex and FH, with magnitude of alcohol analgesia (e.g., increased pain threshold or reduction in pain intensity ratings) as the dependent variable. They will then be entered into simultaneous regression analysis to assess independence of their effects. A positive association between typical drinking and analgesic response to alcohol will provide support for H4. Risk of Type I error will be mitigated through the use of Tukey's HSD. Although not a primary aim, the relationship between individuals' rate of rise of BAC following alcohol consumption and magnitude of alcohol analgesia will be examined in exploratory analyses. For FH+ participants, potential effects of the sex of affected parents and concordance with the participants' sex (i.e., sex-matched vs. unmatched pairs) will also be assessed.

Aim 2. Imaging functional correlates of alcohol analgesia and its modulating factors.

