are disrupted in chronic pain, including default mode network (DMN), salience network (SN), executive control network (ECN), and subcortical limbic network (LN) (Martucci and Mackey, 2016). ICA will be conducted using the voxel-to- voxel processing stream in the CONN toolbox, which involves back-projection of ICs identified across subject and condition to identify spatial components, followed by back-projection of these components to individual subjects (Calhoun et al., 2001). ICs most closely matching networks of interest will be identified based on masks derived from NeuroSynth (Yarkoni et al., 2011). Second, seed-based fcMRI analyses will examine Fishers' r-to-z transformed correlations between the ICA-derived seed ROIs and all other voxels in the brain. Seed-based correlation analyses will be conducted in the Conn Toolbox (Whitfield-Gabrieli & Nieto-Castanon, 2012). Hybrid ICA-seed-based fcMRI has been shown to yield accurate and reproducible results (Franco et al., 2013; Kelly et al., 2010). We will examine interactions of group and condition on connectivity of these resting-state networks using repeated measures GLM, followed by simple main effects decomposition.

Task-based analyses: Alcohol-related changes in BOLD activity in pain- and reward-related brain structures during painful stimulation will be evaluated using a GLM-based approach in SPM12. Following convolution of the canonical hemodynamic response function with the heat stimulation paradigm at the single subject level, group-level effects of dose, sex, and FH on pain-related activations in ROIs and in whole brain will be assessed. To examine the changes in functional connectivity associated with alcohol analgesia, task-based data will be analyzed using the psychophysiological interaction (PPI) pipeline within the Conn Toolbox. PPI is a method of examining task-modulated increases in functional connectivity through GLM by yielding an interaction term (i.e., PPI regressor) from the product of a task's convolved time course (e.g., blocks of noxious thermal stimulation) and the time course from a seed ROI (O'Reilly et al., 2012). Relevant seed ROIs for this analysis will be generated using ICA as described above. We will examine task-dependent functional connectivity in pain- and reward-related networks, both between groups and within conditions, using rmGLM.

Aim 3. Test sex as a moderator of alcohol and FH effects.

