To evaluate Aim 3, sex will be included as a factor of interest in rmGLM analyses described under Aims 1 and 2. A sex by dose interaction such that alcohol consumption produces greater reductions in pain sensitivity and higher VAS ratings of relief for women than men will provide support for H7. Presence or absence of a significant sex by family history by dose interactions on metrics of alcohol analgesia will inform Empirical Question 1. Sex will also be included as a factor of interest in analyses of functional neuroimaging data to determine whether sex and FH of alcoholism interact to determine the effects of acute alcohol administration on pain-related brain processes.

7. Possible Discomforts and Risks:

Psychological Discomforts and Risks. Some aspects of the questionnaires utilized in this proposal may make study participants uncomfortable, especially those dealing with affect or medical history. To ameliorate this possibility, participants will be informed they

can withdraw from the study at any time or skip individual questions that may be upsetting to them.

Acute Alcohol Intake. Alcohol intake may result in dizziness, nausea, and vomiting should a participant tolerate the active dose of alcohol poorly. The risk of these as well as more serious consequences may increase if a participant uses medications that contraindicate the use of alcohol (e.g. benzodiazepines/opioid analgesics). Should a participant experience any of these symptoms, they will be allowed to rest until symptoms subside and will be allowed to withdrawal from the study if desired. We have attempted to minimize this risk by recruiting only those who are regular moderate drinkers and excluding those regularly taking prescription medications that contraindicate the use of alcohol. Ss will be rescheduled if they report having taken prescription or over-the-counter medications that contraindicate alcohol use on the day of testing.

Pregnancy: Alcohol intake is an unacceptable risk in pregnancy. Therefore, anyone of childbearing potential will be tested for pregnancy on the morning of the laboratory session. Positive pregnancy tests will result in exclusion from study and lab staff will assist in making a referral as appropriate. Finally, any documents associated with a participant testing positive for pregnancy will be destroyed without reference to a specific cause.

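### Session order is counterbalanced, but no analysis model contains order or period, so any session shift stays in the alcohol–placebo error term

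*Combined protocol and SAP*

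**What the plan says.** Each participant attends one placebo and one alcohol session, at least 48 hours apart. On order, the Alcohol Administration section says "Session order will be counterbalanced across participants". It does not mention balance within FH or sex groups, or among completers.

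The models in the Data Analysis Strategy are:

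- **Aim 1, behavioural:** "FH status will be included as an independent variable in repeated measures general linear models analyses (rmGLM; SPSS GLM procedure; repeated: dose". Demographic, personality/affective and biomedical variables "will be included as covariates should any be found to correlate significantly with magnitude of alcohol analgesia or relief ratings". Order is not among them.
- **Aim 1, regressions on magnitude of analgesia:** for expectancies and typical drinking, "these measures will be included as independent variables in separate multiple regression analyses including interaction vectors with sex and FH".
- **Aim 2, resting state:** "We will examine interactions of group and condition on connectivity of these resting-state networks using repeated measures GLM".
- **Aim 2, task:** "group-level effects of dose, sex, and FH on pain-related activations in ROIs and in whole brain will be assessed". The imaging nuisance terms are motion, outlier volumes and mean cerebral blood flow.
- **Aim 3:** "sex will be included as a factor of interest in rmGLM analyses described under Aims 1 and 2".

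On baselines, the fMRI Heat Pain Protocol says: "Blocks of thermal stimuli will be delivered to the glabrous skin of the foot at the individually calibrated temperature determined during the screening visit". The QST Procedure section has QST done both before and after the beverage in each laboratory session. The Aim 1 text speaks of increases and decreases in pain measures without naming the reference.

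**The concern.** Participants may respond differently in session 2 than in session 1 through familiarity, habituation or anxiety. That shift enters the alcohol-minus-placebo difference with one sign for alcohol-first participants and the opposite sign for placebo-first participants. Equal orders keep the mean dose effect unbiased, but the shift still inflates the error variance unless order is modelled.

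In-scanner pain ratings, BOLD and connectivity are exposed because scanning follows the beverage and no pre-beverage scan is described. The temperature calibrated at screening is the same in both sessions, so it cancels from the alcohol–placebo difference and cannot remove a session shift.

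Two things are at stake. One is precision, on an FH × dose test that the Power Analysis itself puts at about 54% power. The other is a displaced FH × dose estimate if orders happen to be unevenly split between FH groups.

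**Working it through.** **Inputs from the Power Analysis.** 110 completers, two-tailed tests; d = .28 for alcohol on tolerance and intensity (stated power ~80%); d = .42 for FH on alcohol-related reduction in intensity (stated power ~54%).

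**Assumptions.** Alpha .05; FH split 55/55; d on the scale of the within-person difference; session shift π = 0.2, 0.3 or 0.5 SD of that difference. The documents give none of these. They also give no imaging effect size, so nothing is computed for BOLD or connectivity.

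**The plan's figures with no shift (noncentral t).**

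- Dose: noncentrality .28 × √110 = 2.94, df 109, power 82.9% (stated ~80%).
- FH × dose: .42 × √(55 × 55/110) = 2.20, df 108, power 58.8% (stated ~54%). A 37/73 FH split gives 54.1%.

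**Model.** D = effect ± π (sign set by order) + error with SD 1. Without an order term, the variance over random orders is 1 + π², and the effective d is d/√(1 + π²).

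**Case A: the pilot d excludes period variance; order is not modelled.**

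| π | Variance | FH × dose, 55/55 | FH × dose, 37/73 | Dose |
|---|---|---|---|---|
| 0 | 1.00 | 58.8% | 54.1% | 82.9% |
| 0.2 | 1.04 | 57.2% | 52.5% | 81.4% |
| 0.3 | 1.09 | 55.2% | 50.6% | 79.6% |
| 0.5 | 1.25 | 49.7% | 45.4% | 74.0% |

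At 55/55, FH × dose falls to 54% at π = 0.35, and dose falls to 80% at π = 0.28. With order near-balanced within FH, simulated FH × dose power is about 59%, 58% and 53%, and dose power 81.8%, 80.3% and 76.1%.

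**Case B: the pilot d already contains period variance.** The d net of period is d√(1 + π²): .428, .438, .470 for FH × dose and .286, .292, .313 for dose. Adding order then raises FH × dose power from 58.8% to 60.5%, 62.5% and 68.5% (df 107), and dose power from 82.9% to 84.3%, 86.0% and 90.2% (df 108).

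**Type I error of FH × dose (simulation).**

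| Alcohol-first, per 55 in each FH group | No order term, π = 0.2 / 0.3 / 0.5 | With order term |
|---|---|---|
| 28 v 27 | 4.5 / 4.0 / 2.8% | 4.9–5.0% |
| 30 v 25 (9-point gap) | 5.0 / 4.8 / 4.6% | about 5% |
| 33 v 22 (20-point gap) | 6.4 / 8.2 / 12.8% | 5.0% |

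Averaged over random orders the rate without the term is 4.9–5.2%. At the 20-point gap the spurious d is 2 × π × 0.20 = .08, .12 and .20. A gap of 20 points or more has probability 5.6% if total order is fixed at 55/55, and 4.5% if orders are assigned independently.

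**Unequal orders among completers.** The share of the shift entering the dose estimate is (60 − 50)/110 = 9% at 60/50 and (65 − 45)/110 = 18% at 65/45.

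**Cost of the term when there is no shift.** Losing one degree of freedom moves FH × dose power from 58.82% to 58.81%. A chance FH–order correlation (mean square 1/109) costs about 0.4 points on average. A 20-point gap (r = .2) costs about 1.7 points.

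**The case against.** The strongest reply is that little is shown to be lost. Type I error is near 5% on average, and the FH × dose test is conservative when orders are near-balanced. At 0.2–0.3 SD the stated ~54% and ~80% are still essentially met at 55/55, and in case B no stated power is overstated. All of this stands, and it is why the point is one of efficiency.

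The effect sizes come from pilot pain measures, including QST tolerance, while the firm part of the point concerns the scanner. This also stands: the size for imaging outcomes is unknown.

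In-scanner relief is rated as an effect of the beverage, so it is partly a within-session judgement. A shift in pain need not carry over in full, though a shift in how relief is rated would. Motion, blood flow and repeated mood measures may absorb some of a session shift, but none of them stands in for order.

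The inflated rejection rates need both an uncommon imbalance and a real shift. That is correct. However, recruiting 220 to obtain 110 completers means balance at assignment need not survive to analysis.

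**Conclusion.** The point holds. The design controls order, and the analysis does not use it. It is firm for in-scanner pain ratings, BOLD and connectivity, somewhat weaker for in-scanner relief ratings, and conditional for QST until the reference for change is stated.

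The consequence is lost precision rather than systematic bias. At 55/55 the loss is about 2 to 9 points of FH × dose power for shifts of 0.2 to 0.5 SD in case A; in case B the gain forgone is of similar size. Which case applies cannot be settled, because the pilot is described only in a grant document outside this file. The shift sizes and FH split are assumptions. The term should be added before analysis because it costs almost nothing and also removes displacement from a chance order imbalance between FH groups.

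**What to change.** 1. Enter session order (alcohol first or placebo first) as a between-subjects factor in every repeated-measures GLM, without FH × order or sex × order terms, so that dose × order carries the period effect. If it is entered as a covariate instead, code it −1/+1; with 0/1 coding the dose main effect would refer to one order only. A mixed model with period as a fixed effect is an alternative.
2. Do the same in the task, PPI and resting-state group models, and add order as a covariate in the regressions on magnitude of analgesia.
3. State whether QST outcomes are change from the same-session pre-beverage QST.
4. For participants not yet assigned, balance order within FH × sex cells. Otherwise, report order by FH and sex among completers.
5. As a minor clarification, reconcile Laboratory Sessions, which places all testing in the Center's rooms, with QST Procedure, which places laboratory-session QST in the scanner suite. This bears only on whether session 1 is also a new setting for QST.

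The cost is a change of wording, one to two degrees of freedom, and four order lists in place of one for participants still to be assigned.

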General Approach. For this study of healthy, community-dwelling moderating drinkers, we propose a repeated-measures, double-blind placebo-controlled factorial design with FH of alcoholism (+/-) and sex as between-subjects factors and alcohol administration (Alcohol Dose: placebo, 0.08 g/dL) as a within-subject factor. The study will include equal numbers of men and women. Study procedures will occur in the Center for Pain Research and Behavioral Health of the University of Florida under supervision of the PI (JB). The investigative team, including the PI; Drs. [name], [name], and [name]; and research assistants, will meet on a bi-weekly basis over the course of the project to

ensure successful completion. Recent progress regarding all aspects of the study will be addressed during these meetings, including ongoing review of recruitment practices and behavioral and imaging data quality. Drs. [name], [name], [name], and [name] will also work together to ensure all research assistants are fully trained to conduct the project.

Methods

Participants. Healthy volunteers (N=220; 110 women) will be recruited for the study via flyers, word of mouth, and internet and local radio advertisements with the aim of obtaining 110 completers; 55 women). Individuals aged 21-45 years will be recruited in order to avoid confounding effects of binge-drinking patterns associated with college-aged individuals and the apparent increased susceptibility of older adults to the acute neurobehavioral effects of alcohol (e.g., [name] et al., 2014). We plan to enroll a representative sample of participants from our recruitment area in north central Florida (i.e., 65% white, 23% black, 7% Asian, 5% other), including ~10% identifying as Hispanic or Latino (see targeted recruitment table).

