sessions so that degree of analgesia achieved from beverage consumption can be assessed relative to a personalized baseline. These calibration trials will consist of an ascending series of thermal pulses starting at 43°C and increasing by 1°C until the participant's tolerance is reached. After each pulse, participants will rate pain intensity using a visual analog scale (VAS). The lowest temperature with a VAS score of 5 will be used for thermal stimuli during laboratory sessions. Next, during both screening and laboratory sessions, we will employ a slowly ramping thermal stimulus (.5°C per second starting at 32°C) delivered to the glabrous skin of the foot. Pain ratings (using a 10 cm VAS ranging from "no pain" to "most intense pain imaginable") will be collected every 5 seconds during this process until the participant's tolerance is reached in order to determine temperatures associated with pain threshold (i.e., temperature at which the stimulus first becomes painful) and tolerance (i.e., temperature at which the stimulus becomes unbearable). This protocol also allows for the examination of pain after-sensation following removal of the thermal probe, a construct related to the clinical experience of chronic pain (Staud et al., 2007). To this end, participants will report current pain levels at 15 and 30 seconds following stimulus removal. VASs are considered the "gold standard" for laboratory and clinical pain assessment given that they have a ratio scale (Price et al., 1983) and are able to effectively separate the sensory (i.e., intensity) and affective (i.e., unpleasantness) components of the pain experience. The investigative team has extensive experience with these procedures, and is confident they can be completed safely and effectively. All thermal stimuli will be delivered using a computer-controlled Q-Sense fMRI Compatible thermal stimulator (Ramat Yishai, Israel), a Peltier-element based device. We propose to utilize a thermal stimulus paradigm because the processing of such stimuli is particularly well understood. Such paradigms have been demonstrated in the broader pain literature to be sensitive to group differences (e.g., chronic pain patients vs. healthy controls), as well as experimental manipulations like acute opioid analgesic treatment and placebo induction (e.g., Chung et al., 2007; Sevel et al., 2015; Staud et al., 2012). Furthermore, its use in this study will enhance comparability to previous work. Following each QST measure during laboratory sessions, participants will be provided with a 10 cm VAS assessing perceived relief from pain resulting from beverage consumption (anchored from "No relief at all" to "Most profound relief imaginable"). QST procedures will require approximately 10 minutes. During laboratory sessions, QST procedures will be administered prior to alcohol consumption to function as a point of reference for participants and again approximately 15 minutes after beverage consumption to allow for absorption of alcohol ([name] et al., 2014).

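### Pre-beverage pain threshold and tolerance, measured in both laboratory sessions, are not used in any analysis; their session difference should be a prespecified covariate, and H1 should be tied to FH x dose

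*Combined protocol and SAP*

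**What the plan says.** The General Approach has "alcohol administration (Alcohol Dose: placebo, 0.08 g/dL) as a within-subject factor", and the Alcohol Administration section counterbalances session order. The QST Procedure applies a ramping heat stimulus in both sessions, once before the beverage and once about 15 minutes after it, to find threshold and tolerance temperatures. The first run has one stated role: "QST procedures will be administered prior to alcohol consumption to function as a point of reference for participants".

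In the Data Analysis Strategy, Aim 1, "FH status will be included as an independent variable in repeated measures general linear models analyses (rmGLM; SPSS GLM procedure; repeated: dose"). Dose is the only repeated factor. The pain measures are listed as dependent variables without saying whether post-beverage values or changes are meant. Demographic, personality/affective and biomedical variables "will be included as covariates should any be found to correlate significantly with magnitude of alcohol analgesia or relief ratings"; no QST value is on that list. The expectancy and typical-drinking regressions take "magnitude of alcohol analgesia (e.g., increased pain threshold or reduction in pain intensity ratings) as the dependent variable", with no formula. Aim 3 looks for "A sex by dose interaction such that alcohol consumption produces greater reductions in pain sensitivity", again with no baseline term.

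Support for H1 is described as "A main effect of FH status such that FH+ individuals have greater magnitude of alcohol analgesia". The Power Analysis instead gives about 54% "power to detect interactive effects of FH and dose on these measures".

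**The concern.** Each completer provides four laboratory QST runs, and the plan says how to use only the dose contrast. The two pre-beverage runs carry information about how sensitive a person was on that day, before any alcohol. Part of the noise in the alcohol-minus-placebo difference may be exactly that day-to-day variation, and it can be removed at almost no cost. This matters most for FH x dose, where the plan already expects low power.

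The H1 wording is a linked point. If the main effect of FH is taken from the rmGLM on undifferenced scores, it compares FH groups averaged over alcohol and placebo. That is a comparison of overall pain sensitivity, not of analgesia.

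**Working it through.** **Inputs.** From the documents: 110 completers (Participants), two-tailed tests, FH effect d = .42 on alcohol-related reduction in pain intensity, d < .26 on threshold and tolerance, and about 54% power for FH x dose (all Power Analysis). Assumed: alpha .05, FH split 55/55 (not stated), pilot d not already referenced to a pre-beverage value, and c from .2 to .6.

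**The plan's figure.** With two dose levels, FH x dose is a two-sample t-test on each person's alcohol-minus-placebo difference. The noncentrality is d x sqrt(n1 n2/(n1+n2)).
- d = .42, 55/55: .42 x sqrt(27.5) = 2.20 on 108 df, power 58.8%.
- d = .42, 37/73: power 54.1%, which matches the plan.
- d = .26, 55/55: .26 x 5.244 = 1.36, power 27.2%.

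The FH split, alpha and the standardiser of d are not given, so the gap between 54% and 58.8% is not shown to be an error.

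**Effect of the covariate.** Let Y be the alcohol-minus-placebo difference after the beverage, X the same difference before it, and c their correlation. Adjusting Y for X multiplies the residual variance by 1 - c^2. The effect size becomes d/sqrt(1 - c^2), and the residual df fall from 108 to 107. At c = .5, for example, .26/sqrt(.75) = .300.

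| c | adjusted d (from .26) | power |
|---|---|---|
| unadjusted | .260 | 27.2% |
| 0 | .260 | 27.2% |
| .2 | .265 | 28.1% |
| .3 | .273 | 29.4% |
| .5 | .300 | 34.5% |
| .6 | .325 | 39.3% |

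If d = .42 referred to ramp ratings, the 55/55 figures would be 58.8% unadjusted and 61/63/71/78% adjusted at c = .2/.3/.5/.6.

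**Form of the covariate.** Three choices matter.
- *Uncentred.* In simulation with no dose effect, centring X on its sample mean gave Type I error for dose of about 6%, 9% and 12% at c = .3/.5/.6. Left uncentred, it stayed at 5%.
- *One difference, not two baselines.* FH is a reported trait, so conditioning on overall sensitivity can change what FH x dose estimates. In a simulation where FH groups differed by .5 SD, alcohol shrank deviations from the average level by 50%, and c was .5, the mean FH x dose estimate was -.247 unadjusted, -.248 with the difference, and -.050 with both baselines.
- *Screening values do not replace it.* A single screening value is the same for both sessions and cancels from the alcohol-minus-placebo difference.

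**The H1 term.** Assume between-person SD 1 and within-person variance .5 per session, with 55/55. The session difference then has SD sqrt(.5 + .5) = 1, and the session average has SD sqrt(1 + .25) = 1.118. Simulation gives:
- FH groups .5 SD apart in overall sensitivity, no FH effect on analgesia: the FH main effect on the undifferenced outcome (.5/1.118 = .45) rejects in about 65%, FH x dose in about 5%.
- True FH x dose of d = .42, no overall difference: the main effect (.21/1.118 = .19) rejects in about 16%, FH x dose in about 59%.

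**The case against.** The plan never presents the pre-beverage run as an analysis baseline. It is there to orient participants, who then rate relief from the beverage, and a placebo-controlled crossover contrast needs no baseline. That stands, and it is why nothing here is called bias.

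The pilot d = .42 is for pain intensity. The clearest intensity outcome is the rating after each heat block in the fMRI Heat Pain Protocol, which has no pre-beverage counterpart. Ramp ratings are collected to locate threshold and tolerance, and no ramp-rating summary is named as an outcome. That stands too. A reader might infer a gain from 59% to as much as 78%, but the documents support that only if d = .42 refers to ramp ratings.

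A reader might also infer that the plan would analyse raw pre-to-post changes and lose power that way. No section proposes this. The reference that the QST Procedure does name for degree of analgesia is the screening calibration, which sets each person's stimulus temperature. It gives no formula for threshold or tolerance.

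On H1, a main effect of FH on a magnitude score is the same thing as FH x dose, and the Power Analysis supports that reading. So the documents do not show that H1 will be tested wrongly. The same sentence also covers expectancy, a screening measure for which a main effect is the right term. What remains is wording that permits the wrong test on the pain measures.

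**Conclusion.** The point holds as an inexpensive gain in precision and a clarification. Pre-beverage threshold and tolerance are collected twice and used nowhere. At d = .26, 55/55 and two-sided alpha .05, using them raises FH x dose power from 27% to 28-29% for c of .2 to .3, and to 35-39% for c of .5 to .6. The plan gives no value of c. The gain would be smaller or nil if the pilot d is already baseline-referenced. Because .26 is an upper bound, these tests stay underpowered either way. The gain for the expectancy and typical-drinking regressions is not quantified here. The 65% and 16% figures for the H1 term rest on assumed variances and describe only the literal reading of the Aim 1 sentence.

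**What to change.** In the Data Analysis Strategy:

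1. For QST threshold and tolerance (and ramp ratings, if a summary of them is analysed), define analgesia as the alcohol-minus-placebo difference in post-beverage values.
2. Enter the same measure's alcohol-minus-placebo difference in pre-beverage values as a prespecified covariate, uncentred and as a single term. Exempt it from the rule that admits covariates only if they correlate significantly. Use it in the rmGLM (Aims 1 and 3) and in the expectancy and typical-drinking regressions.
3. In Aim 1, state that H1 is tested on the pain measures by FH x dose, or equivalently by the FH effect on the alcohol-minus-placebo difference. Keep the main effect of FH for expectancy.

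The cost is wording and one degree of freedom; the plan already collects the data. If c is 0 the loss is negligible (27.2% with and without the covariate at d = .26).
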